## 7.2 Secondary Efficacy Variables

- Change from baseline in ppFEV1 at visits 3 and 4 (weeks 1 and 2)
- Change from baseline in FEV1 at visits 3, 4 and 5
- Change from baseline in forced vital capacity (FVC) and percent predicted FVC (ppFVC) at visits 3, 4 and 5
- Change from baseline in 25-75% forced expiratory Flow (FEF25-75) at visits 3, 4 and 5
- Change from baseline in Cystic Fibrosis Questionnaire-Revised (CFQ-R) (respiratory and physical domains) at visit 5.

### 7.3 Safety Variables

- Incidence of treatment-emergent AEs (TEAEs)
- Changes in vital signs
- Changes in clinical laboratory tests, including urine and blood electrolytes
- Changes in electrocardiograms

### 7.4 Pharmacokinetic Variable:

- Systemic exposure to SPX-101 (Cohort 1 only)

### 7.5 Exploratory Variables:

- Incidence of pulmonary exacerbation, as defined by Fuchs (1994)
- Incidence of concomitant hypertonic saline use

### 7.6 Predetermined Covariates and Prognostic Factors

In Cohort 1, baseline lung function ppFEV1 categories (percent predicted forced expiratory volume in 1 second between 40.0% and 55.0% vs between 55.1% and 80.0%) will be included as a covariate in the model of the analysis of covariance (ANCOVA).

In Cohort 2, the use (yes/no) of concomitant hypertonic saline and baseline ppFEV1 will be covariates in the ANCOVA model.

## 8.0 Definitions and Data Derivations

### Baseline

For two sequential cohorts, each cohort will have its own baseline. Unless otherwise specified, baseline is defined as the last non-missing value before the first dose of study drug (SPX-101 or placebo). Baseline values will be assessed at Visit 2 (Day 1) in this study. If Visit 2 measures are missing, corresponding variables at screening visit will be used as baseline.

For spirometry endpoints, the baseline is defined as the last non-missing value before the first dose of study drug (SPX-101 or placebo) at Visit 2 (Day 1) for primary analysis. The average of screening and Visit 2 (Day 1) values will also be derived for exploratory purpose.

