#### 9.4.3 Randomization Criteria (Assessed at Visit 2)

On Day 1 of the study, after completion of the screening period, the following criteria will be assessed to determine subject eligibility for randomization:

1. Continue to meet the entrance criteria
2. Negative serum (Visit 1) and urine (Visit 2 pre-randomization) pregnancy test result for all female subjects of childbearing potential

3. Stable FEV1 at Visit 2 defined as FEV1 within  $\pm 15\%$  of the relative change between the Visit 1 and Visit 2 best FEV1. Relative change is defined as follows:

$$\frac{\text{FEV}_1 \text{ (Screening; Visit 1)} - \text{FEV}_1 \text{ (Visit 2)}}{\text{FEV}_1 \text{ (Screening; Visit 1)}} \times 100$$

4. No new intervening illnesses since Screening (Visit 1), and the subject's CF is still stable in the judgment of the Investigator  
 5. No clinically significant laboratory or ECG abnormalities that pose a significant risk to the subject, per the judgment of the Investigator

Note: A subject may be re-screened once if they fail to meet randomization criteria for any reason. If this is the case, a new consent form must be signed, and a new screening number will be used.

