### 11.3 Pulmonary Function Tests

Spirometry will be performed at all clinic visits using equipment provided by the centralized spirometry vendor, Biomedical Systems (BMS). Spirometry will be performed in accordance with ATS/ERS guidelines and the GLI predictors of spirometric lung volume normal ranges [2; 3]. At Visit 2, spirometry will be performed pre-dose, and postdose at 30 minutes, 2 hours, and 4 hours postdose after completion of administration of the study drug. At all other visits, only pre-dose spirometry will be performed. The following parameters will be recorded:

- Absolute FEV1 and ppFEV1
- Absolute FVC and ppFVC

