## 6.1 Sample Size Considerations

In Cohort 1, the study was planned for a minimum of 39 subjects per cohort to be enrolled. The subjects will be randomized in a 1:1:1 ratio to one of the two treatment groups or placebo. The sample size of 39 subjects provided 70% power for the Analysis of Variance (ANOVA) to detect a difference range of 4.5% to 6% in the change from baseline in ppFEV1 and FEV1 between the 2 treatment groups versus placebo, with the two-sided alpha level of 0.15 assuming a common standard deviation of 7%. The attrition rate is expected to be minimal given the 4 week treatment duration.

In Cohort 2, a total of 45 subjects will be randomized in a 2:1 ratio to SPX-101 120 mg BID or placebo. The sample size of 45 subjects will provide 88% to 97% power to detect a difference range of 6% to 8% in the change from baseline in ppFEV1 between the treatment group versus placebo, with the 1-sided alpha level of 0.1 assuming a common standard deviation of 7.58%. The estimated treatment difference and standard deviation are based on the Cohort 1 results from the 120 mg SPX-101 dose group and placebo, among subjects with baseline ppFEV1 between 50.0% and 80.0%, since this reflects the subjects enrolled in Cohort 2.

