### 12.6.1 Primary Variable

#### Primary Efficacy Analysis

The primary efficacy endpoint is the change from baseline in ppFEV1 at visit 5 (week 4). The change from baseline in ppFEV1 at each visit (Weeks 1, 2, and 4) will be summarized and compared between each treatment group and placebo. No imputation of missing data will be done for this analysis.

The comparison between each treatment group and placebo will be evaluated by using an analysis of covariance (ANCOVA) model, which will include treatment as the factor, and the stratification factor as a covariate (i.e., baseline lung function categories [ppFEV1 40.0% to 55.0% or 55.1% to 80.0% for Cohort 1] and the concomitant use of hypertonic saline for Cohort 2). Also included in the ANCOVA model for Cohort 2 is baseline ppFEV1. Descriptive statistics will include the number of observations, unadjusted mean, standard deviation, median, first quartile, third quartile, minimum and maximum, and least squares mean. Treatment differences from placebo will be presented and estimated by least squares means from the analysis model along with 95% confidence intervals and associated 2-sided p-values, which are presented for descriptive purposes.

Sponsor: SPYRYX Biosciences

Protocol no: SPX-101-CF-201

---

As described in the power and sample size calculations in Section 6.1, Cohort 1 will be evaluated for success using a two-sided 0.15 significance level. Cohort 2 will be evaluated for success using a one-sided (upper) 0.10 significance level. For Cohort 2, both the one-sided p-value and the lower bound (i.e. one-sided 90% confidence interval) will be presented.

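### Cohort 2's primary model adjusts for Visit 2 ppFEV1 only and leaves the screening ppFEV1 unused: a modest, optional gain in precision forgone, not a bias

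*SAP*

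**What the plan says.** **Baseline.** SAP 8.0 takes the primary spirometry baseline as the last non-missing pre-dose value at Visit 2 (Day 1). It then adds: "The average of screening and Visit 2 (Day 1) values will also be derived for exploratory purpose". Neither SAP section 12 nor section 13 describes an analysis that uses this average.

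**Model.** SAP 7.6 states: "In Cohort 2, the use (yes/no) of concomitant hypertonic saline and baseline ppFEV 1 will be covariates in the ANCOVA model". SAP 12.6.1 repeats this for the primary analysis. The Cohort 2 MMRM and the multiple-imputation ANCOVA in the same section use the baseline value and do not name the screening value.

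**Availability of a second reading.** Protocol 11.3 says: "Spirometry will be performed at all clinic visits using equipment provided by the centralized spirometry vendor". Visit 1 is such a visit, 3 to 28 days before Visit 2. The Cohort 2 ppFEV1 range of 50% to 80% is assessed on screening spirometry (SAP 6.2). Protocol 9.4.3 also requires the Visit 2 FEV1 to lie within 15% of the Visit 1 value, and the subject to "Continue to meet the entrance criteria". A subject cannot be properly randomized without both readings.

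**Design figures.** SAP 6.1 plans 30 active and 15 placebo subjects and claims the following, in points of ppFEV1: "The sample size of 45 subjects will provide 88% to 97% power to detect a difference range of 6% to 8". The inputs are an SD of 7.58 and a one-sided alpha of 0.10. SAP 12.6.1 carries the same alpha into the success criterion: "Cohort 2 will be evaluated for success using a one-sided (upper) 0.10 significance level".

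**The concern.** A single visit's ppFEV1 measures a subject's usual level with some error, and that error enters the change score directly. Adjusting for the Visit 2 value removes part of it. A second pre-treatment reading can remove more, to the extent that it says something about the Week 4 value that Visit 2 does not. That reading is already in the database and the SAP already plans to average it with Visit 2, yet the model that decides Cohort 2 leaves it out.

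What is at stake is the width of the confidence interval and a little power, in a cohort with only about 15 placebo subjects. Protocol 7.3.2 gives the variability seen in Cohort 1 as a reason for running this cohort, so precision obtainable from existing data is worth considering.

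**Working it through.** **1. The plan's own figure.** Inputs from SAP 6.1: 30 active and 15 placebo (45 at 2:1), SD 7.58, one-sided alpha 0.10.

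- SE = 7.58 × √(1/15 + 1/30) = 2.40.
- Noncentral t with 43 df: power 88.4% at 6 points and 97.8% at 8 points. The normal approximation gives 88.9% and 98.0%.
- The stated 88% to 97% is reproduced. A two-sided 0.10 test would give 79.3% and 94.9%, so the stated figure is one-sided, as the SAP says.

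**2. Reference case without entry rules.** If the Visit 1, Visit 2 and Week 4 values all share one correlation r, adding Visit 1 to a model that has Visit 2 multiplies the residual variance by (1 + 2r)/(1 + r)².

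- r = 0.5: 2.0/2.25 = 0.889.
- r = 0.9: 2.8/3.61 = 0.776.

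This ignores the entry rules and assumes independent visit errors, so it is too favourable here.

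**3. With entry rules, by simulation.** Assumptions, none of them given in the documents:

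- True ppFEV1 level: mean 65, between-subject SD 8 or 12.
- SD of change 7.58 before selection, with 25% to 100% of that variance being visit-to-visit noise.
- Entry: ppFEV1 50-80 at both visits, and Visit 2 within 15% of Visit 1. Applying the range at Visit 2 is an inference from Protocol 9.4.3. Dropping it hardly matters: with independent noise at 100%, the variance ratio is 0.922 instead of 0.920 at SD 8, and 0.910 instead of 0.906 at SD 12.

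For power, each residual SD is rescaled so that the SD of change in selected subjects is 7.58. The df are 41 with two covariates and 40 with three. Example, SD 8, all noise, independent errors: the SD of change after selection is 6.92. Visit 2 only: 6.63 × 7.58/6.92 = 7.26, SE 2.30, power 90.4%. With Visit 1 added: 6.36 × 7.58/6.92 = 6.97, SE 2.20, power 92.1%.

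| Visit errors | True SD, noise share | Residual SD, Visit 2 only → plus Visit 1 | Variance reduction | Power at 6 points |
|---|---|---|---|---|
| Independent | 8, 100% | 6.63 → 6.36 | 8% | 90.4% → 92.1% |
| Independent | 12, 100% | 6.79 → 6.47 | 9% | 89.4% → 91.5% |
| Independent | 12, 25% | 7.52 → 7.33 | 5% | 88.6% → 89.7% |
| Adjacent-visit correlation 0.3 | 12, 100% | 7.09 → 6.96 | 3.6% | 89.2% → 90.0% |
| Adjacent-visit correlation 0.3 | 8, 25% | 7.52 → 7.44 | 2.1% | 88.7% → 89.1% |
| Adjacent-visit correlation 0.5 | 12, 100% | 7.22 → 7.17 | 1.5% | 89.1% → 89.4% |

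Reductions come from unrounded SDs. Where the readings follow a pure first-order autoregressive process with no stable subject level, Visit 1 adds nothing and the reduction is 0%.

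**4. In subjects.** In the independent case, 45/0.95 = 47.4 and 45/0.907 = 49.6, about 2 to 5 extra subjects. At the Cohort 1 estimate for this dose, 5.19 points (Protocol 7.3.2), power in that case goes from 81-83% to 82-85%.

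**5. Cost.** With the residual SD held at 7.58, going from 41 to 40 df changes power at 6 points from 88.42% to 88.41%.

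**The case against.** The strongest reply is that nothing is defective. The baseline is prespecified and agrees with the protocol's definition (13.6.2). The Cohort 2 model already adjusts for continuous baseline ppFEV1, which is more than the protocol's primary model asks for (13.6.4.1). The stated power reproduces. A further baseline covariate could be suggested for almost any trial. **This stands**, and it is why the point is optional.

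The size is uncertain. The documents give no visit correlations, and independent errors are the favourable case. The design also gives a reason to expect less from Visit 1. For inhaled-antibiotic users, Day 1 is timed to the start of a cycle (Protocol 9.5.7), whereas Visit 1 can fall anywhere in the preceding 3 to 28 days, so the two readings are not strictly interchangeable. **This also stands**, and the range has to reach down to zero.

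Three stronger readings are tempting, and the documents support none of them.

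- *A noisy baseline that is also an entry criterion biases the comparison.* The criterion is applied before dosing and equally to both arms, so it affects precision only.
- *The 15% stability rule shows noise larger than the effect.* At ppFEV1 65 it allows 0.15 × 65 = 9.75 points, but that is an eligibility limit for one subject, not an estimate of measurement error. The Visit 2 value is also the best of a session, not one manoeuvre.
- *The gain is 11-22%, as in step 2.* That ignores the entry rules, which trim what Visit 1 can add.

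Finally, SAP 12.6.1 moves the primary test to an ANOVA with treatment only, or to Wilcoxon-Mann-Whitney, if its assumption checks fail. Neither uses covariates, so in that event there is no gain.

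**Conclusion.** The point holds as a modest loss of precision. A pre-treatment ppFEV1 that every properly randomized Cohort 2 subject has is left out of the primary model, and the planned average is attached to no analysis. Using the screening value would lower residual variance by about 5-9% if visit errors are independent, and by about 0-4% if they are serially correlated. In power at 6 points that is a move from about 89-90% to 90-92% in the first case, and a gain of 0 to about 0.8 points in the second.

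These figures assume that 7.58 is the SD of the raw change; the SAP does not say whether it is that or a model residual SD. They also assume between-subject SDs of 8 to 12 and the entry rules as read above. The direction is secure, since at worst the covariate is close to neutral. The treatment comparison is valid as planned. Cohort 1 has already been analysed and is not affected.

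**What to change.** Before Cohort 2 database lock, amend SAP 7.6 and 12.6.1:

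- Keep change from the Visit 2 value as the endpoint, and keep Visit 2 ppFEV1 and hypertonic saline use as covariates.
- Add screening (Visit 1) ppFEV1 as a second continuous lung-function covariate in the primary ANCOVA. Do the same in the MMRM and the multiple-imputation ANCOVA.
- Define the reading as the last valid screening-period value before Visit 2, from the screening that led to randomization. This covers the re-test allowed in Protocol 10.1 and the single re-screen allowed in 9.4.3. Because Protocol 9.5.9 allows Visit 2 to be repeated once, say also that a reading from a superseded Visit 2 is not a screening reading.
- State what is done if the screening value itself serves as baseline because Visit 2 is missing, as the general rule in SAP 8.0 allows. The two covariates would then be the same number for that subject.
- Either name an analysis for the screening/Visit 2 average or delete it.

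The cost is a few SAP sentences and one model degree of freedom. No new data are needed, and no properly randomized subject is lost. Alpha, sample size and endpoint are unchanged.

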### Change from Baseline

Change from baseline (CFB) will be calculated as (value at post-baseline visit – value at baseline). CFB will be calculated for subjects with both a baseline and post-baseline value as applicable. Percent CFB will be calculated as (CFB/baseline)\*100, where applicable. If a baseline or post-baseline value has not been recorded for a parameter, then CFB will not be calculated for that parameter. Subjects with missing CFB values will be excluded from analyses in which CFB is the endpoint unless otherwise noted.

### Study Day 1

The first day of study product administered.

## Study Day

Study day is defined as the number of days from Study Day 1.

- Before Study Day 1: Study Day = (Date of Interest – Date of Study Day 1)
- On or After Study Day 1: Study Day = (Date of Interest – Date of Study Day 1) + 1

Therefore, the day prior to Study Day 1 is -1.

## Study Completion

A subject is considered completed the study if a subject is not terminated early and completes Visit 5 (Day 29).

## Prior and Concomitant Medications

Prior medications will be any medication with a start date before the first day of treatment that has been discontinued prior to the first dose of study treatment.

Concomitant medications are defined as any medications ongoing at the start of treatment or with a start date on or after the first dose date but on or prior to the last dose of treatment date.

## Treatment-emergent Adverse Event (TEAE)

A TEAE is defined as an AE which begins or an aspect of medical history that increases in severity after the first dose of study drug until the final study visit phone call on Day 31. Adverse Events will be considered treatment-emergent if they have missing or partial start dates for which it cannot be determined whether the AE started before or after the first dose of study medication.

## Adverse Events with Outcome of Death

Any AE with an outcome of “fatal” will be considered as AE with an outcome of death.

## **Imputation of AE (for determination of TEAE only) and concomitant medication start and stop dates:**

### **Start Date:**

If only ‘day’ is missing, and the month and year are not the same as the month of first dose, then impute day with ‘01’. Otherwise, if the month and year are the same as the first dose date, use the first dose date.

If ‘day’ and ‘month’ are missing, and ‘year’ is not missing, then impute month and day with month and day of the first dose date (assuming same ‘year’).

If ‘day’ and ‘month’ are missing and ‘year’ is not missing and is not the same year as first dose date, then impute with ‘01’ for both ‘day’ and ‘month’. If the start date is completely missing, it will be set to the first dose date.

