### **Stop Date:**

If only ‘day’ is missing, impute day with last day of the month.

If ‘day’ and ‘month’ are missing, and ‘year’ is not missing, then impute month with ‘12’ and day with ‘31’ (or date of study discontinuation/completion if earlier than 12-31 and year is the same as the year of discontinuation).

If the stop date is completely missing, it will be set to the date of study discontinuation/completion. A stop date will not be applied to ongoing AEs.

The imputed dates will be used to assess whether AEs should be considered as treatment-emergent and if medications should be included in the safety summaries as prior or concomitant, however the original, partial dates will be included in data listings. The duration of AEs will be derived as the AE end date (including imputation date for incomplete AE end date) –AE onset date (imputed date for incomplete AE onset date) +1.

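### SAP 8.0 can give a medication a Day 1 start although its recorded stop precedes first dose, and so class as concomitant a drug known to be prior

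*SAP*

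**What the plan says.** SAP Section 8.0 (imputation of AE and concomitant-medication dates, Start Date) assigns the first dose date in three situations:

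- Nothing is known of the start: "If the start date is completely missing, it will be set to the first dose date".
- Only the day is missing, in the month and year of first dose: "Otherwise, if the month and year are the same as the first dose date, use the first dose date".
- Only the year is known and it is the year of first dose: "then impute month and day with month and day of the first dose date".

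Other partial start dates are filled with 01 for the missing parts. None of the three branches refers to the stop date, and the Stop Date rules add no cap or exception. Those rules do say that imputed dates determine "if medications should be included in the safety summaries as prior or concomitant". They also define AE duration as end date minus onset date plus 1, using imputed dates where needed.

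The definitions that receive these dates are in the same section. A prior medication is "any medication with a start date before the first day of treatment that has been discontinued prior to the first dose of study treatment". A concomitant medication is one ongoing at the start of treatment, or one "with a start date on or after the first dose date but on or prior to the last dose of treatment date". For adverse events, the TEAE definition defaults to treatment-emergent only for missing or partial start dates "for which it cannot be determined whether the AE started before or after the first dose".

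**The concern.** Assuming on-treatment timing is a sensible default when timing is unknown. If the recorded stop precedes first dose, the timing is known: the start must also precede first dose. The three branches ignore that information. They produce a record whose start is later than its stop and pass it to a definition of concomitant whose second limb never looks at the stop.

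At stake are descriptive tables: the prior and concomitant medication summary by arm (SAP 12.5) and possibly the number of subjects taking inhaled antibiotics during treatment (SAP 12.2, Cohort 2). The SAP also ends up with two rules for one adverse-event record. The TEAE definition would leave out an event known to have ended before dosing, while the imputation rule gives it a Day 1 onset.

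**Working it through.** The plan states no figure here, so there is none to reproduce. The check applies the written rules literally.

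**Notation.** F = first dose date, L = last dose date, S = start date (imputed if incomplete), E = stop date.

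- Prior: S < F and E < F.
- Concomitant: ongoing at F, or F ≤ S ≤ L.
- AE duration (defined for AEs only): E − S + 1.

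**General result.** In the three branches S = F. The prior condition S < F fails and F ≤ S ≤ L holds, so the record is concomitant whatever E is. If E is k days before F (k ≥ 1), an AE with those dates has duration (F − k) − F + 1 = 1 − k: zero for k = 1, negative for k ≥ 2.

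**Illustration.** Assumed dates: F = 20 Sep 2018, L = 27 days later. The last column applies only if the record were an AE.

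| Start as recorded | Stop | Imputed start | Class as a medication | Known status | E − S + 1 |
|---|---|---|---|---|---|
| missing | 10 Sep 2018 | 20 Sep 2018 | concomitant | prior | −9 |
| 2018 | 31 Aug 2018 | 20 Sep 2018 | concomitant | prior | −19 |
| Sep 2018 | 10 Sep 2018 | 20 Sep 2018 | concomitant | prior | −9 |
| Sep 2018 | 19 Sep 2018 | 20 Sep 2018 | concomitant | prior | 0 |
| Aug 2018 | 10 Sep 2018 | 1 Aug 2018 | prior | prior | 41 |
| 2017 | 10 Sep 2018 | 1 Jan 2017 | prior | prior | 618 |

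The first four rows are misclassified. The last two are not, because their partial dates share neither the month nor (when only the year is given) the year of first dose.

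**Can such records occur?** Protocol 13.1 has previous medications taken within 28 days of screening coded, and screening is at most 28 days before Day 1. Drugs stopped up to about 28 + 28 = 56 days before dosing are therefore in scope: back to 26 Jul 2018 in this illustration, which covers every stop date in the table. Protocol 9.4.1, criterion 8a, admits subjects who alternate monthly between two inhaled antibiotics or go on and off one. A course ending shortly before Day 1 is thus a natural candidate if its start date is incomplete.

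**Size per subject.** Cohort 2 plans 45 subjects at 2:1, so 15 on placebo and 30 on SPX-101. One misclassified subject moves a table percentage by 1/15 = 6.7 points or 1/30 = 3.3 points. SAP 12.5 counts a subject once per drug and once per class, so the percentage moves only if that subject has no other qualifying record of the drug or class. For example, a subject switching between two antibiotics at Day 1 would inflate the count for the stopped drug but not for a class that contains both.

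**Check of the fix.** Replacing S by the earlier of S and E makes the first four rows prior and leaves the last two unchanged.

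**The case against.** The strongest reply is that few records can qualify. Protocol 9.4.1, criterion 8, requires CF medication to be unchanged for 28 days before screening with no change expected, and Protocol 9.5.7 continues the usual regimen during the study. Long-standing CF drugs with a forgotten start date will mostly be ongoing at Day 1, where concomitant is the right answer. Short courses allowed under criterion 8 must have ended more than 28 days before screening, outside the coding window. The error needs a drug stopped inside a narrow window, with a usable stop date and an incomplete start. An inhaled antibiotic between cycles or a non-CF drug could meet that, but the documents give no count. This stands, and it limits the point to a minor one.

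A reader might also infer more than the text supports:

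- *That the three branches misclassify every record they touch.* They do so only when the stop precedes first dose.
- *That adverse-event tables are materially affected.* Protocol 12.1 sends AEs before randomization to medical history, and SAP 12.8.1 does the same for conditions before study drug. What remains is an SAE reported from consent onward, or a pre-dose event entered as an AE by mistake, that also lacks a full start date. No summary listed in SAP 12.8.1 uses duration. The negative durations show that the rule is inconsistent; they do not measure the medication error, because no medication duration is defined.
- *That efficacy subgroups shift.* Cohort 2 hypertonic saline status comes from the randomization system (SAP 8.0), and the antibiotic-cycle subgroup is assigned by sponsor review (SAP 12.6.4). Dornase alfa use must be stable for at least 28 days before screening with no change anticipated, so a pre-dose stop would sit badly with eligibility.
- *That the SAP 12.2 antibiotic count is certainly affected.* The SAP does not say how that count is derived.

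**Conclusion.** The point holds as a rule that gives the wrong answer as written, rather than as missing detail. When a medication's stop is recorded before first dose and its start is incomplete in one of the three ways, SAP 8.0 classes it as concomitant although it is known to be prior. The same gap could give a rare adverse-event record a Day 1 onset and a zero or negative duration, in conflict with the SAP's own TEAE definition.

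The importance is low. The consequence is confined to descriptive tables, the number of records is unknown and probably small, and the primary ppFEV1 result does not change. The conclusion assumes that the rules are programmed as written; an unwritten stop-date check in the programs would remove the error but should then be in the SAP.

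**What to change.** Add to the date-imputation rules in SAP 8.0:

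1. An imputed start date may not be later than the recorded or imputed stop date; if it is, set it to the stop date.
2. Any medication with a stop date before first dose is prior, and any event with a stop date before first dose is not treatment-emergent, however incomplete the start date.

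This keeps the on-treatment default where timing really is unknown and brings the imputation rule into line with the TEAE definition. It costs a short SAP addition and about one line in the date-imputation program, with no change to data collection.
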